#### 9.3.2.3 Example of Specimen Label

The following image is an example of a tissue specimen label printed on a standard Avery label that is 1" high and 2.625" wide.

The QR code in the above example is for the Specimen ID shown on the second line.

**NOTE:** The QR code label is currently under development at Theradex as of 31-Aug-2018; therefore, labels generated by the STS for this study may not include a QR code.

The second line item from the end includes four data points joined together:

1. Tissue only: Primary (P), Metastatic (M), Normal (N) tissue indicated at the beginning of the specimen ID; this field is blank if not relevant (e.g., for blood)
2. Block ID or blank if not relevant
3. SPID (Surgical Pathology ID) or blank if none
4. The last alpha-numeric code is protocol specific and is only included if the protocol requires an additional special code classification

The last line on the example label is for the handwritten date and optional time.

#### 9.3.2 Overview of Process at Treating Site

##### 9.3.2.1 OPEN Registration

All registrations will be performed using the Oncology Patient Enrollment Network (OPEN)

system. OPEN communicates automatically with the Interactive Web Response System (IWRS) which handles identifier assignments, any study randomization and any prescribed slot assignments. If specimen analysis is required to determine eligibility, the protocol will be setup with multi-step registration.

Registration without eligibility specimen analysis:

1. Site enters registration data into OPEN during one or more steps.
2. IWRS receives data from OPEN, generates the Patient Study ID and the Universal Patient ID, both of which are sent back to OPEN.
3. IWRS sends all applicable registration data directly to Rave at the end of the final registration step.

Any data entry errors made during enrollment should be corrected in Rave.

### 9.3.2.2 Rave Specimen Tracking Process Steps

**Step 1:** Complete the **Histology and Disease** form (but do not upload reports until a specimen label can be applied to them) and the Baseline forms regarding **Prior Therapies**. Enter the initial clinical specimen data:

- **Specimen Tracking Enrollment** CRF: Enter Time Point, Specimen Category, Specimen Type, Block number, Tissue type, Surgical Path ID, number of labels needed (include extra labels to apply to reports to be uploaded). CRF generates unique Specimen ID.

**Step 2:** Print labels using report in EDC and collect specimen.

- Label specimen containers and write collection date on each label.
- After collection, store labeled specimens as described in Section.
- Apply an extra specimen label to *each* report before scanning. Return to the **Histology and Disease** form to upload any initial Pathology, Radiology, Molecular Reports (up to 4), Surgical reports and Pathology Verification form (when applicable). Return to **Specimen Tracking Enrollment** CRF to upload any molecular report (one per specimen) and/or specimen specific pathology or related report (one per specimen). Uploaded reports should have PHI data like name, mailing address, medical record number or SSN redacted. Do not redact SPID, block number or relevant dates.

**Step 3:** Complete specimen data entry.

- **Specimen Transmittal** Form: Enter Collection date and time and other required specimen details.

**Step 4:** When ready to ship, enter shipment information.

- **Shipping Status** CRF: Enter tracking number, your contact information, recipient, number of containers and ship date once for the 1st specimen in a shipment.
- **Copy Shipping** CRF: Select additional specimens to add to an existing shipment

referenced by the tracking number.

**Step 5:** Print shipping list report and prepare to ship.

- Print two copies of the shipping list, one to provide in the box, the other for your own records.
- Print pathology or other required reports to include in the box. Be sure the printed copy includes the specimen label.

**Step 6:** Send email notification.

- For only one of the specimens in the shipment, click “Send Email Alert” checkbox on the **Shipping Status** CRF to email recipient.

**Step 7:** Ship the specimen(s).

## 9.4 Shipping of Biospecimens from Clinical Sites to the ETCTN Biorepository

### Shipping of Specimen(s):

**Ambient temperature shipments:** include core biopsies in formalin, blood in cfDNA Streck tube, and blood in green-top tubes (at Baseline only) in one shipment to the Biorepository on Monday through Wednesday, using the same box to ship that was used to receive the kit contents. Note: If blood is collected on Wednesday through Friday then it may be shipped separately from the tissue, on the day of collection.

- Place specimens (separated by specimen type) in zip-lock bags.
- Place zip-lock bags in a biohazard envelope containing absorbent materials. Next, place the biohazard envelope into a Tyvek envelope. Expel as much air as possible before sealing each envelope.
- Place the Tyvek envelope into the shipping container. In warm months, place a cold (NOT frozen) gel pack into the container with the specimens.
- Insert a copy of the shipping manifest and any other required paperwork, including operative and radiology, and/or pathology reports, into the container with the specimens. Place paperwork in a plastic zip-lock bag to prevent potential contamination in case of specimen leakage.
- Place the cover on the shipping container. Tape the shipping container closed with durable tape.
- Attach the FedEx air bill and attach to top of shipping container.
- Attach an Exempt Human Specimen sticker to the side of the shipping container.
- Make arrangements for courier pickup.

**Frozen shipments:** Serum (four aliquots) and snap-frozen core biopsies may be combined as one shipment on dry ice to the biorepository. Ensure that sufficient dry ice is included to completely encase the specimens to maintain specimen integrity during shipment. Frozen specimens may be shipped on Monday through Thursday.

Pre-fill the shipping container about 1/3 full with dry ice.

Place specimens (separated by specimen type) in zip-lock bags.

Place zip-lock bags in a biohazard envelope containing absorbent materials. Next, place the biohazard envelope into a Tyvek envelope. Expel as much air as possible before sealing each envelope.

Place the Tyvek envelope into the shipping container and fill the container to the top with additional dry ice.

Insert a copy of the shipping manifest and any other required paperwork, such as a pathology report, into the container with the specimens. Place paperwork in a plastic zip-lock bag in case of sample leakage.

Place the cover on the container. Tape the shipping container closed with durable tape.

Complete a FedEx air bill and attach to top of shipping container.

Complete a dry ice label.

Attach the dry ice label and an Exempt Human Specimen sticker to the side of the shipping container.

Make arrangements for courier pickup.

In cases of delays in shipment, store at -80 C.

## 9.6 Integral Laboratory or Imaging Studies

NONE.

## 9.7 Investigational Device Information

NOT APPLICABLE.

A series of horizontal black bars of varying lengths, with a small yellow bar at the top left, obscuring several lines of text.

## 9.9 Exploratory/Ancillary Correlative Studies

### 9.9.4 Whole Exome and RNA Sequencing

Specimens: Whole blood in NaHep (green-top) tubes at Baseline; tissue biopsy (-ies) fixed in formalin and submitted in 70% Ethanol to the ETCTN Biorepository at Baseline. Upon receipt, DNA will be extracted from K2-EDTA whole blood, aliquoted and stored in a -80°C freezer until distribution for testing. Tumor tissue will be processed and embedded. Slides will be cut, and the first section will be stained with H&E for pathology quality control review to assess tumor content; unstained slides will be macrodissected, if needed, and then DNA and RNA will be co-extracted, aliquoted, and stored in a -80°C freezer until distribution for testing.

This has been identified as the highest-priority exploratory study for the use of tumor biopsy tissue, after the integrated immunohistochemical studies.

Site(s) Performing Correlative Study: Sequencing will be performed at the Molecular Characterization Laboratory at NCI-Frederick. This laboratory is under the direction of Dr. [name].

#### 9.9.5 Immune phenotyping

Lymphocyte subsets in both tumor isolates and peripheral blood will be analyzed by multi-color flow cytometry.

#### 9.9.6 Additional Correlative Studies

Plasma processed from cfDNA Streck tubes will be stored for future analyses of serum HSV status and circulating nucleic acids in blood plasma.

If sufficient tumor tissue is obtained, then additional exploratory assays will be conducted to quantitate T-VEC DNA in tissue samples using a PCR-based method.

### 9.10 Exploratory Imaging Correlatives

#### Pelvic MRI

Outcome Measure: MRI pelvis will be obtained in all patients (as part of standard of care) at baseline and prior to surgery (wk 21 -25) or 8-10 weeks from completion of chemoradiation (in patients not undergoing surgery).

Method: The current MDACC imaging protocol for primary rectal cancer incorporates the use of high resolution T2 weighted images acquired in the axial plane perpendicular to the plane of the tumor. These images are acquired using a phased array coil and small field of view (16-18cm), which generates an in-plane resolution of 0.6-0.7 mm. In addition to anatomic information provided by T2 weighted images, we obtain diffusion weighted images which are used to generate apparent diffusion coefficient (ADC) maps. These are surrogates for tumor cellularity and treatment response. This imaging technique enables an accurate assessment of depth of tumor invasion beyond the muscularis propria and relationship to the mesorectal fascia (potential CRM) with high accuracy and inter-observer agreement. In addition the T stage is assessed with an accuracy of 67-83% and moderate inter-observer agreement. In terms of assessment of response to chemo radiation; morphologic MR markers have been proposed based on high

resolution T2 weighted images to distinguish well from poor responders. However this approach is subject to significant inter-observer variability. When supplemented with DWI there is a significant improvement in accuracy and the prediction of complete response.

In the current trial, we tumors will be characterized into good and poor responders to enable binary comparison. mrTRG is based on similar principles to the pathologic TRG and is based on the degree of tumor replaced by fibrotic stroma on post-treatment pelvic MRI. mrTRG-5 (no fibrosis, only tumor signal visible), mrTRG4 (predominantly tumor signal with minimal fibrotic single) will be defined as poor responders whereas mrTRG-1 (no tumor signal) to mrTRG-3 (50% or greater fibrotic stroma) will be defined as good. For the purposes of CRM, a margin greater than or equal to 1 mm between the tumor and the resection margin will be defined as clear (good responder) and the rest as poor responders. Prognosis of good responders including DFS, OS and local recurrence will be compared to that of poor responders. Furthermore, mrTRG will be compared to ypTRG to validate its accuracy. Two radiologists with extensive experience with rectal MRIs (Drs. [name] & [name]) will read all the scans to minimize inter-observer variability.

## 9.11 Exploratory genomic studies

Genomic testing results including but not limited to RAS, RAF mutations and / or microsatellite instability will be utilized to correlate with radiographic & pathologic response to talimogene laherparepvec based therapy, survival including DFS and OS. Mutation testing will be performed utilizing institutional next generation sequencing platform. Microsatellite status will be determined by either analysis of mismatch repair protein expression by immunohistochemistry or by microsatellite testing by polymerase chain reaction.

## 10. STUDY CALENDAR

Baseline evaluations (including laboratory tests) need not be repeated at start of protocol therapy if done within 1 week. Scans, x-rays must be done  $\leq$ 4 weeks prior to the start of therapy. In the event that the patient's condition is deteriorating, laboratory evaluations should be repeated within 48 hours prior to initiation of the next cycle of therapy. **On-study tests/visits** that must occur within a defined time frame shall have a standing window of allowance that is equal to +/- 2 days for any laboratory testing and +/- 4 days for any re-staging/disease assessment criteria. Surgery in eligible patients may occur within a window of +/- 2 weeks

	Pre-Study	Week 0	Wk 1	Wk 2	Wk 3	Wk 4	Wk 5	Wk 6	Wk 7	Wk 8 g	Wk 9/10 g	Wk 12/13 – 19/20 g m	Wk 27 - 36	Wk 27 & beyond f	Off Study c
TALIMOGENE LAHERPAREPVEC b		X			X		X		X						
FOLFOX A			X		X		X		X			X			
RT k												X			
Surgery n													X		
Informed consent	X														
Demographics	X														
Medical history	X														
Concurrent meds h	X		X-----									X			
Physical exam	X	X	X		X		X		X	X	X	X			X
Vital signs	X	X	X		X		X		X	X	X	X			X
Height	X			X		X		X	X	X	X	X			
Weight	X		X		X		X		X	X	X	X			X
Performance status	X		X		X		X		X	X	X	X			X
CBC w/diff, plts	X	X	X		X		X		X	X	X	X			X
PT / INR / aPTT d	X	X													
Serum chemistry a	X	X	X		X		X		X	X	X	X			X
Tumor Markers e	X												X		
EKG (as indicated)	X														
Adverse event evaluation h	X		X-----									X			X
Tumor measurements	X		In addition to baseline, tumor measurements will be obtained prior to surgery (wk 21-25). Documentation (radiologic) must be provided for patients removed from study for progressive disease.												X
Radiologic evaluation	X		In addition to baseline, radiographic evaluation will be obtained prior to surgery (wk 21-25).												X
B-HCG	X b														
CORRELATIVE STUDIES															
Archival Tissue	X														

Pelvic MRI	X										X	
Tumor Biopsies i			X j					X			X	
Peripheral Blood l	X							X			X	
	A:	FOLFOX: Dose as assigned; administration schedule										
	B:	TALIMOGENE LAHERPAREPVEC: Dose as assigned; administration schedule										
	a:	Albumin, alkaline phosphatase, total bilirubin, bicarbonate, BUN, calcium, chloride, creatinine, glucose, LDH, phosphorus, potassium, total protein, SGOT [AST], SGPT [ALT], sodium.										
	b:	Serum pregnancy test (women of childbearing potential).										
	c:	Off-study evaluation.										
	d:	At baseline and subsequently as required per treating physician's discretion										
	e:	Tumor markers include CEA and CA 19-9 at baseline, if above normal, repeat within 1 week of day 1 of radiation and with presurgical evaluation										
	f:	Chemotherapy regimen / dosing / schedule, imaging and follow up post-surgery per treating physician's discretion										
	g:	Evaluation by any involved provider (medical oncology / surgical oncology and / or radiation oncology)										
	h:	Adverse event evaluation until 4 weeks out of surgery										
	i:	Optional										
	j:	In patients without adequate archival tissue										
	k:	Radiation will be 25 Gy over 5 fractions.										
	l:	Refer to Section 9 for tube types and volumes.										
	m:	On day 1 of each cycle of FOLFOX										
	n:	In those deemed needing surgical resection per clinical evaluation; not mandatory per protocol										

## 11. MEASUREMENT OF EFFECT

Although the clinical benefit of these drugs has not yet been established, the intent of offering this treatment is to provide a possible additional therapeutic benefit to the known benefit of concurrent chemoradiation therapy to primary rectal cancer for palliation of symptoms and reduction in tumor burden. Thus the patient will be carefully monitored for tumor response and symptom relief in addition to safety and tolerability. Patients with measurable disease will be assessed by standard criteria. For the purposes of this study, patients will be re-evaluated prior to surgery. In patients with completely resected tumors, further evaluation for disease recurrence will follow standard NCCN/ASCO guidelines and can be modified based on clinical symptoms at the treating physician's discretion. In surgically resected patients, disease-free survival and overall survival will be evaluated. In patients with metastatic disease at the time of treatment, overall survival will be evaluated in addition to response at distant sites (by diagnostic imaging) due to potential abscopal effect.

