## SCHEMA

- Patients with rectal adenocarcinoma either locally advanced or metastatic rectal adenocarcinoma requiring chemoradiation to the primary lesion are eligible.
- Patients with locally advanced rectal adenocarcinoma (T3 or T4, at risk of having a positive surgical radial margin and/or N+), or patients with metastatic disease requiring chemoradiation.
- Patients will be treated with FOLFOX chemotherapy x 4 doses over 8 weeks (weeks 1-8) followed by short course radiation over 5 days (weeks 9 or 10).
- Subsequently, starting approximately 2 weeks after finishing short course RT, patients will receive FOLFOX chemotherapy x 4 doses (weeks 12 / 13 – 19 / 20). While surgical resection of the primary is not mandatory, those requiring surgery will undergo resection 8-16 weeks later (weeks 27 - 36) and / or further systemic therapy per treating physician's discretion.
- Talimogene laherparepvec will be administered via endoscopy by a qualified physician for a total of 4 doses at the following time points: a) week prior to c1 FOLFOX b) weeks 3, 5 and 7 during FOLFOX
- Dose escalation will be done using a 3 + 3 design over 2 cohorts and a total of 15 patients

Dose level+	TALIMOGENE LAHERPAREPVEC Dose (PFU/ml)	Capecitabine (mg/m  po bid on days of radiation)	Radiation	Comments
1	1x 10  , 1x 10  , 1x 10  , 1x 10 	825	50.4 Gray in 28 fractions	Completed prior to protocol amendment 1/23/21
1 (amended)	1x 10  , 1x 10  , 1x 10  , 1x 10 	N/A	25 Gray in 5 fractions	To be implemented if DLTs noted with DL 2
2	1x 10  , 1x 10  , 1x 10  , 1x 10 	N/A	25 Gray in 5 fractions	

will be treated at MTD.

Dose limiting toxicities (DLTs) will be captured until completion of FOLFOX chemotherapy (weeks 18/9) and will be graded according to the CTCAE ver 5.0.

#Patients with inadequate archival tissue for integrated biomarker analysis

^As part of pre-surgical evaluation or at a corresponding time point in patients not undergoing surgery

+Dose escalation will be done using a 3+3 design for a total of 15 patients that will be treated at MTD

TVEC = talimogene laherparepvec

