## 3. PATIENT SELECTION

### 3.1 Inclusion Criteria

3.1.1 **For dose escalation:** Patients must have A) histologically or cytologically confirmed low lying (up to 6 cm of anal verge) rectal adenocarcinoma eligible for radiation therapy to rectal tumor, B) If the treatment is palliative in the metastatic setting, no additional requirements for tumor size or nodal involvement is needed. C) If the treatment is in the neoadjuvant setting, the tumor must ALSO be high-risk locally advanced rectal cancer defined as T3-4, N+, and/or at risk for a positive radial margin (as determined by the surgeon)

3.1.2 **For dose expansion:** Patients must have A) histologically or cytologically confirmed rectal adenocarcinoma eligible for radiation therapy to rectal tumor irrespective of location from anal verge, B) If the treatment is palliative in the metastatic setting, no additional requirements for tumor size or nodal involvement is needed. C) If the treatment is in the neoadjuvant setting, the tumor must ALSO be high-risk locally advanced rectal cancer defined as T3-4, N+, and/or at risk for a positive radial margin (as determined by the surgeon)

3.1.3 Age  $\geq$ 18 years. Because no dosing or adverse event data are currently available on the use of talimogene laherparepvec in combination with chemotherapy in patients  $<$ 18 years of age

3.1.4 ECOG performance status  $\leq$  2 (Karnofsky  $\geq$ 60%, see Appendix A).

3.1.5 Patients must have normal organ and marrow function as defined below:

- Absolute neutrophil count (ANC)  $\geq$ 1.5x10^9/L
- Hemoglobin  $\geq$ 9 g/dL
- Platelets  $\geq$ 100,000 x10^9/L
- Serum bilirubin  $\leq$ 1.5x institutional upper limit of normal (ULN)  
(except patients with Gilbert's Syndrome, who can have total bilirubin  $<$  3 mg/DL)
- Aspartate aminotransferase (AST) and alanine aminotransferase (ALT)  $\leq$ 2.5x institutional ULN
- Serum creatinine  $\leq$ 1.5 mg/dL *OR* calculated creatinine clearance (Cockcroft-Gault formula)  $\geq$ 50 mL/min *OR* 24-hour urine creatinine clearance  $\geq$ 50 mL/min
- Prothrombin time (PT)/International normalized ratio (INR) and partial thromboplastin time (PTT)  $\leq$ 1.5x institutional unless the subject is on anticoagulant therapy (If the subject is receiving anticoagulant therapy, PT, and aPTT must be within therapeutic range of intended use of anticoagulants)

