## 5.6 Duration of Follow Up

Patients will be followed for 30 days after removal from study or until death, whichever occurs first. Patients who have undergone curative resection will be monitored for a minimum of 2 years (and up to 5 years) for disease recurrence. Patients removed from study for unacceptable adverse event(s) will be followed until resolution or stabilization of the adverse event.

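### Section 11 plans overall survival in metastatic patients, but Section 5.6 follows those without curative resection only to 30 days after an undefined removal date

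*Combined protocol and SAP*

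**What the plan says.** **Who is in the trial.** Section 3.1 admits palliative metastatic patients to both escalation and expansion: "If the treatment is palliative in the metastatic setting, no additional requirements for tumor size or nodal involvement is needed". Resection is optional. The Schema says "While surgical resection of the primary is not mandatory", and a footnote to the study calendar (Section 10) says "In those deemed needing surgical resection per clinical evaluation; not mandatory per protocol". Some treated patients may therefore never have a curative resection.

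**What is to be estimated.** Section 11 makes two survival commitments. The first is "In surgically resected patients, disease-free survival and overall survival will be evaluated". The second is "In patients with metastatic disease at the time of treatment, overall survival will be evaluated in addition to response at distant sites". Section 13.4 names the Kaplan-Meier method for survival, without a time origin, a censoring rule or a minimum follow-up.

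**How long patients are followed.** Section 5.6 has three sentences on this:
- Default: "Patients will be followed for 30 days after removal from study or until death, whichever occurs first".
- After curative resection: "Patients who have undergone curative resection will be monitored for a minimum of 2 years (and up to 5 years) for disease recurrence".
- After removal for toxicity: "Patients removed from study for unacceptable adverse event(s) will be followed until resolution or stabilization of the adverse event".

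**When removal happens.** Section 5.5 asks for the reasons and dates of stopping therapy and of leaving the study as separate items. It does not say when a patient who finishes treatment leaves the study. The calendar has an undated off-study column and an open-ended column from week 27. The footnote to the latter is worded for post-surgical care and leaves follow-up to the treating physician. No row of the calendar collects vital status.

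**The concern.** An OS evaluation needs deaths, or at least known survival status, over a useful period. The patients for whom Section 11 plans it are, unless curatively resected, given only the default rule of Section 5.6, and that rule runs from an event that the protocol does not date.

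Two things are at stake. First, the length of survival follow-up in metastatic patients is left to each site's reading of when removal occurs, and may be too short for a useful OS estimate. Second, the rule ties the end of follow-up to the patient's course. The calendar foresees removal from study for progressive disease. Such a patient would be censored about 30 days later, just when the risk of death is likely to have risen. Kaplan-Meier estimation assumes that censored patients share the later risk of those who remain. If patients who have just progressed do worse than that, the curve is too high, and not merely imprecise.

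**Working it through.** The documents give no OS event count, target, landmark time or assumed median, so there is no planned figure to reproduce. The check is a comparison of texts, followed by an illustration.

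**Comparison of texts**

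| Patient group | Survival endpoint | Follow-up in Section 5.6 |
|---|---|---|
| Curatively resected | DFS and OS (Section 11; objective 1.3.4) | 2 to 5 years, worded for recurrence |
| Metastatic, no curative resection | OS (Section 11 only) | 30 days after removal or until death; after removal for toxicity, until the event resolves or stabilizes |

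No other section fills the second row. Section 5.1.1.2 foresees endoscopic surveillance in patients who forgo surgery, and Section 11.1 asks that progression be documented even after treatment stops. Neither sets a survival schedule.

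**Illustration of follow-up length**

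The inputs are:
- the 30 days and the 2 years, from Section 5.6;
- weeks 27 to 36, the surgery window in the Schema and the calendar;
- a month of 30.4375 days.

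The assumption, which is not in the documents, is that a patient without curative resection is removed from study in the same weeks in which others have surgery.

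- Without curative resection, months from week 0 = (7 × week + 30) / 30.4375.
  - Week 27: 219 / 30.4375 = 7.2.
  - Week 36: 282 / 30.4375 = 9.3.
- Curatively resected, with the 2 years counted from surgery, months from week 0 = (7 × week + 730.5) / 30.4375.
  - Week 27: 919.5 / 30.4375 = 30.2.
  - Week 36: 982.5 / 30.4375 = 32.3.
- Ratio for the same week: 30.2 / 7.2 = 4.2, and 32.3 / 9.3 = 3.5.

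**Illustration of deaths observed**

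A further assumption is exponential survival with a median OS of 12 to 36 months. No median is given in the documents. The share of deaths seen by time t is 1 − 0.5^(t / median).

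| Follow-up from week 0 | Median 12 months | Median 24 months | Median 36 months |
|---|---|---|---|
| 7.2 months | 34% | 19% | 13% |
| 9.3 months | 41% | 24% | 16% |
| 24 months | 75% | 50% | 37% |

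In the first two rows follow-up ends before the assumed median, so a Kaplan-Meier median would not be expected to be reached. The bias from censoring after progression cannot be sized from the documents. Only its likely direction can be stated.

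**The case against.** The strongest reply is that the protocol does not make follow-up short; it leaves it open. Removal from study is recorded apart from the end of therapy, the calendar runs on past week 27, and a site could keep a metastatic patient on study for a long time. This stands. A reader might infer that metastatic OS will certainly have little data, and the documents do not support that. They support the statement that the length is indeterminate and that the written rule permits an early end.

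A reader might also take removal at the end of FOLFOX, about week 20, as the natural case and so find a larger gap. The documents fit this poorly. Section 9.1 plans specimens at weeks 30 to 35, a Schema footnote provides a matching time point for patients without surgery, and Section 5.1.1.2 foresees surveillance in them. Pairing the earliest removal with the latest surgery would overstate the contrast, so the comparison here uses the same weeks for both groups.

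A third inference would be that the responder comparison in Section 13.4 suffers from unequal follow-up. That depends on unresected patients being included. The comparison covers DFS and local recurrence, refers to the resection margin and sets mrTRG against pathological regression. Read with objective 1.3.4, the resected population is the more natural reading. Some ambiguity remains, because objectives 1.3.1 and 1.3.3 and Section 9.11 name no population and Section 9.10 also takes MRI in unresected patients. A clarifying sentence is enough.

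It is also fair to say that metastatic OS has no counterpart in objective 1.3.4, which is limited to curative resection, so the conflict rests on one sentence in Section 11. Section 2.4 reports that all first-cohort patients had surgery, and the number of metastatic patients without curative resection is not known. These facts limit the importance of the point but do not reconcile the two sections.

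**Conclusion.** The inconsistency is real and minor. Section 11 commits to OS in metastatic patients, and the only follow-up rule does not secure the data for it unless the patient has a curative resection. Follow-up is indeterminate, may end soon after treatment, and for patients removed at progression would end at a point where censoring is likely informative and would tend to make OS look too favourable.

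Under the assumed removal at weeks 27 to 36, the gap is about 7.2 to 9.3 months against about 30 to 32 months, a factor of roughly 3.5 to 4.2. These figures rest on an assumed removal date, and the shares of deaths rest also on assumed medians and exponential survival; neither set is a prediction for this trial. The direction of the censoring bias rests on the judgement that risk of death rises after progression.

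The endpoint is exploratory. Nothing here touches the dose-limiting toxicity assessment or the MTD, and the documents give no ground for reading it that way.

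**What to change.** **Preferred.** In Section 5.6:
- define removal from study, including for patients who complete treatment;
- add vital-status follow-up by chart review or telephone for treated patients without curative resection, for example on the two-to-five-year schedule already used after curative resection;
- name survival status, and not only recurrence, for resected patients.

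Add a survival row to the calendar in Section 10. The cost is a wording change and periodic status checks in at most 21 patients, the accrual ceiling in Section 13.2. Whether consent already covers longer contact cannot be judged from the pages available.

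**Otherwise.** Delete the metastatic OS sentence from Section 11, and state in Section 13.4 that the DFS and OS comparisons are limited to curatively resected patients. This adds no work, but the metastatic OS evaluation is given up.

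Either change concerns data collection and analysis only, and leaves treatment as it is.
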